## **11.5 Safety Analysis**

The evaluation of SYNT001 based on vital signs, physical examination, ECGs, clinical safety laboratory tests, the incidence of AEs, TEAEs, and SAEs will be summarized by dose and dose regimen, severity, and relationship to study drug.

Treatment-emergent AEs will be summarized using the Medical Dictionary for Regulatory Activities (MedDRA®; Version 19 or higher) System Organ Class (SOC) and preferred term, classified from verbatim terms. The incidence and percentage of subjects with at least 1 occurrence of a preferred term will be included, using the most severe grade. The number of events per preferred term will also be summarized. Causality (relationship to study drug [related/not related]) will be summarized separately.

TEAEs, SAEs, and AEs leading to withdrawal, dose modification, or treatment discontinuation will be listed by subject per SOC and preferred terms. Duration of AEs will be determined and included in listings, along with action taken and outcome.

Laboratory results will be summarized by time point, dose, and dose regimen. Incidence of laboratory abnormalities will be summarized. The worst on-study grade after the first dose of study drug will be summarized. Results for variables that are not coded will be presented in the listings as below, within, and above the normal limits of the central laboratory.

Vital sign measurements and change from baseline will be summarized at each scheduled time point by cohort using descriptive statistics.

Arithmetic mean of parameters from triplicate ECG will be calculated first for each participant at each planned time point. Then summary statistics of ECG test parameters (mean of triplicate) and change from baseline to each post-dose time point will be calculated. Shift tables for ECG test result category change (normal, abnormal, clinically abnormal) from pre-dose to each post-dose time point showing number and percentage of subjects with movement between categories will be presented by treatment group. Frequency and percentage of subjects experiencing potential QTc prolongation (QTcF >450) will be summarized at each time point by cohort.

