1. INTRODUCTION

This study is being conducted to evaluate the safety, tolerability, pharmacokinetics (PK), pharmacodynamics (PD), immunogenicity, and effects of intravenous (IV) SYNT001 in subjects with warm autoimmune hemolytic anemia (WAIHA).

Results obtained from the analysis outlined in this document will become the basis for the final Clinical Study Report (CSR) for this protocol. This SAP supersedes the statistical considerations identified in the protocol; where considerations are substantially different, they will be so identified. If additional analyses are required to supplement the planned analyses described in this SAP, they may be performed and will be identified in the CSR.

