4.7.2 Clinical Laboratory Tests

Laboratory results, percentage change and absolute change from baseline will be summarized by cohort, visit and time point using descriptive statistics. Incidence of laboratory abnormalities and laboratory NCI CTCAE (Version 4.03) will be summarized. Shift tables of CTCAE Grade for chemistry parameters (Normal, Grade 1, Grade 2, Grade 3, Grade 4, Grade 3/4, Total, Missing) from baseline to each post-baseline time point showing number and percentage of subjects with movement between categories will be presented. The worst on-study grade after the first study drug administration will also be summarized.

Baseline is defined as the Day 0 (pre-dose) measurement. If the baseline measurement is missing, the last measurement prior to the first study drug administration will be used.

Results, normal limits of the local laboratory, and abnormality flags will be listed.

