4.7.3 Physical Examination, Vital Signs, and Electrocardiogram Findings

The number and percentage of subjects with normal, abnormal and clinically significant, abnormal but not clinically significant physical exam findings will be summarized by visit and dose.

Vital sign measurements and change from baseline will be summarized at each scheduled time point by cohort using descriptive statistics. Baseline is defined as the Day 0 (pre-dose) measurement. If the baseline measurement is missing, the last measurement prior to the first study drug administration will be used.

The arithmetic mean of parameters from triplicate ECGs will be calculated first for each participant at each planned time point. Then summary statistics for ECG test parameters (mean of triplicate) and change from baseline to each post-dose time point will be calculated. Shift tables for ECG test result category changes (normal, abnormal not clinically significant, abnormal clinically significant) from pre-dose to each post-dose time point showing number and percentage of subjects with changes between categories will be presented by cohort.

The number and percentage of subjects experiencing potential QTcF prolongation (QTcF > 450, >480 and >500 msec, and change from baseline in QTcF >30 and >60 msec) will be summarized at each time point by cohort.

Actual sampling times that are outside the scheduled sampling times window described in [Table 5](#) will be excluded from summary statistics.

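### SAP 4.7.3 counts QTcF limit crossings only time point by time point, so no planned table gives the number of subjects who crossed a limit at any time after dosing

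*Protocol*

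**What the plan says.** ECGs are one component of the primary safety endpoint, which is to be summarized by dose and dosing regimen (Protocol Section 3; SAP 2.1.1). SAP Section 1 settles which text governs: "This SAP supersedes the statistical considerations identified in the protocol". The operative rule is therefore SAP 4.7.3.

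- **Unit of analysis.** "The arithmetic mean of parameters from triplicate ECGs will be calculated first for each participant at each planned time point". Protocol 11.5 says the same.
- **Threshold counts.** The SAP tabulates "The number and percentage of subjects experiencing potential QTcF prolongation", with absolute limits of 450, 480 and 500 msec, and closes the sentence with "change from baseline in QTcF >30 and >60 msec) will be summarized at each time point by cohort". Protocol 11.5 has only the 450 limit, in the same layout: "Frequency and percentage of subjects experiencing potential QTc prolongation (QTcF >450) will be summarized at each time point by cohort".
- **Shift tables.** ECG category shifts also run from pre-dose to each post-dose time point separately.
- **Timing exclusion.** The last sentence of SAP 4.7.3 removes from summary statistics "Actual sampling times that are outside the scheduled sampling times window described in" Table 5. For ECGs that window is 5 minutes after the end of infusion, ±10 minutes.
- **Unscheduled ECGs.** Neither document has a rule for them.

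Other safety data are treated differently. For laboratory results SAP 4.7.2 adds: "The worst on-study grade after the first study drug administration will also be summarized". SAP 4.7.1 counts each subject with at least one occurrence of an adverse event term.

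**The concern.** For a drug given repeatedly, the natural safety question is how many subjects had a prolonged QTcF at some point after starting treatment. A set of per-visit counts does not answer it. Counts at different visits cannot be added, because the table does not show whether the same subject recurs or a new one appears. One subject with a persistent prolongation and several subjects with one crossing each can produce identical rows.

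The second issue is which ECGs reach the table. A dosing-day reading taken outside its window is removed from the summaries by rule. An ECG done between visits has no row to sit in and no rule that assigns it to one. Such ECGs may well be the informative ones, since they can be prompted by symptoms or by an earlier abnormal reading.

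**Working it through.** The plan states no QTcF rate, sample size calculation or error rate, so there is no figure of its own to reproduce. The check is whether the planned table determines the any-time count.

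**Inputs**

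- Cohort sizes: up to 8 and up to 12 (Protocol 6.8).
- Cohort 1 post-dose ECGs: Days 0 (after the infusion), 12, 28 and 56, so 4 time points (Protocol Table 2). The Day 12 ECG is taken only if that visit is on site (Table 2, footnote g). Without it there are 3.
- Cohort 2 post-dose ECGs: Days 0 (after the infusion), 14, 28, 91 and 140, so 5 time points (Protocol Table 3). On the alternative weekly schedule Day 28 becomes Day 21, still 5 (Table 10).

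**Bounds.** Let c_t be the number of subjects over a limit at time point t, n the cohort size and A the number over it at any post-dose time point. Then

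max(c_t) ≤ A ≤ min(n, Σ c_t).

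The lower bound is reached if the same subjects recur, the upper if all are different. With an assumed c_t = 1 at every time point:

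| Cohort | Table shows at each time point | A, lowest | A, highest |
|---|---|---|---|
| 1, 4 time points | 1/8 = 12.5% | 1/8 = 12.5% | 4/8 = 50% |
| 1, without Day 12 | 1/8 = 12.5% | 1/8 = 12.5% | 3/8 = 37.5% |
| 2, 5 time points | 1/12 = 8.3% | 1/12 = 8.3% | 5/12 = 41.7% |

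The planned display is the same across each row's whole range.

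**Dependence on the number of ECGs.** If each time point had the same crossing probability p, independently, the any-time probability over k time points would be 1 − (1 − p)^k. The values of p are assumed:

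| p | k = 4 | k = 5 |
|---|---|---|
| 2% | 7.8% | 9.6% |
| 5% | 18.5% | 22.6% |
| 10% | 34.4% | 41.0% |

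Readings within a subject are likely to be positively correlated, which would pull these values down. The table shows only the direction: the any-time figure exceeds the per-visit figure and grows with k.

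**Reach of the window rule.** Table 5 covers dosing visits and has a single ECG row. The exclusion therefore bears on Days 0 and 28 in Cohort 1 and on Days 0, 14 and 28 (or 21) in Cohort 2. A reading more than 5 + 10 = 15 minutes after the end of infusion falls outside.

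**The case against.** The strongest reply is that the information is not lost. All captured clinical data are listed (SAP Section 4), and with at most 20 subjects and four or five scheduled post-dose ECGs each, anyone can read the count off the listing. In addition, SAP 3.2.6 sets normal QTcF at 450 msec or below and sends ECG abnormalities that appear after therapy to the adverse event form, where SAP 4.7.1 counts subjects with at least one occurrence. A reader might infer from the per-visit layout that the study report could never yield the number. The documents do not support that, because both routes exist. What remains is that a hand count is not a planned result. The adverse event route depends on recording and coding, and preferred-term counts do not reproduce the 480, 500, 30 and 60 msec limits that the SAP chose.

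A reader might also infer that the plan excludes unscheduled ECGs. No text says so. The reference to planned time points governs how triplicates are averaged, and the threshold sentence speaks only of time points. The documents are silent on unscheduled ECGs; the only explicit exclusion is of out-of-window measurements.

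Three further points carry weight. The study is descriptive, and the stopping rules in Protocol 8.5 rest on adverse events, not on this table. The table shells are in separate documents (SAP Section 6) that may already contain such a row, and SAP Section 1 allows supplementary analyses. Nor would an any-time row make the cohorts comparable: they share only Days 0 and 28 as post-dose ECG days, or only Day 0 on the weekly schedule, and they differ in the number of ECGs.

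**Conclusion.** The point holds as a reporting gap of modest weight. The protocol and SAP plan QTcF threshold counts only at each time point, and those counts do not determine how many subjects crossed a limit after dosing. The laboratory and adverse event sections do plan subject-level summaries, so the omission is specific to ECGs.

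The size can only be illustrated. The bounds rest on full cohorts and an invented pattern of one crossing per time point, and their upper ends are arithmetic extremes, not expectations. That an off-schedule prolonged reading may enter no count rests on the written exclusion for dosing-day readings outside the window and on the absence of any rule for unscheduled ones. Nothing here affects sample size, error rates or trial conduct.

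**What to change.** In SAP 4.7.3, keep the by-time-point rows and add one block:

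- By cohort and in total, the number and percentage of subjects whose maximum QTcF after the first dose exceeds 450, 480 and 500 msec, and whose maximum change from baseline exceeds 30 and 60 msec.
- Denominator: subjects with at least one post-dose ECG. This needs stating, because SAP 4.1 otherwise defaults to the whole analysis population and a subject without an ECG would count as a non-event.
- For this block, include out-of-window and unscheduled ECGs, as an exception to the section's closing sentence. Use the triplicate mean where there is one. Flag any crossing that rests on a single tracing, or show the count with and without those.

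The cost is one table block and a few SAP sentences, with no new data or procedures. There are three drawbacks. On the same denominator the any-time percentage is at least as high as any per-visit percentage. It rises with the number of ECGs per subject (up to 4 scheduled in Cohort 1, 5 in Cohort 2), so a footnote should caution against direct comparison. Single tracings are noisier than triplicate means, which is why they need the flag.

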## **11.6 Pharmacodynamic Analysis**

Disease activity marker results (hematocrit, hemoglobin, platelet count, reticulocyte count, LDH, haptoglobin, total and indirect bilirubin, and direct Coombs test) will be summarized by dose and dose regimen. Descriptive statistics of PD will include mean, SD, median, minimum, and maximum.

## **11.7 Immunogenicity Analysis**

Immunogenicity results will be summarized by cohort and time point. Descriptive statistics will include mean, SD, CV, median, minimum, and maximum.

## **11.8 Interim Analysis**

No formal interim analysis is planned. Safety and PD results will be examined on an ongoing basis for making dose-escalation decisions; no statistical analyses are planned for aiding these dose-escalation decisions.

## 12. DATA QUALITY ASSURANCE

All data will be entered in a validated electronic data capture system using single data entry. Standard procedures (including following data review guidelines, manual clinical review based on subject profiles, computerized validation to produce queries, and maintenance of an audit file which includes all database modifications) will be followed to ensure accurate data. Clinical personnel will review all data listings for outliers, data inconsistencies, and spelling errors.

During the study, a study site monitor will make site visits to review protocol compliance, compare eCRFs against individual subject medical records, assess drug accountability, and ensure that the study is being conducted using pertinent regulatory requirements. eCRF entries will be verified with source documentation. The review of medical records will be performed in a manner to ensure that subject confidentiality is maintained. Checking the eCRFs for completeness, clarity and cross checking with source documents is required to monitor the progress of the study. Direct access to source data is also required for inspections and audits, and will be carried out giving due consideration to data protection and medical confidentiality. Each Investigator will have assured the Sponsor of full access to complete source data for study participants and associated necessary support at all times.

In addition to routine monitoring procedures, audits of clinical research activities in accordance with standard operating procedures (SOPs) may be performed to evaluate compliance with the principles of GCP. A regulatory authority may also wish to conduct an inspection (during the study or even after its completion). If a regulatory authority requests an inspection, the Investigator must immediately inform the Sponsor that this request has been made. Study conduct may be assessed during the study by a Clinical Quality Assurance representative(s) to ensure that the study is conducted in compliance with the protocol. This designee, as well as the site monitor, will be permitted to inspect the study documents (study protocol, eCRFs, investigational product accountability, original study-relevant medical records). All subject data will be treated confidentially. During the clinical study, access will be available to the Sponsor or their designee (eg, contract research organization [CRO]) to view the eCRFs after completion of the individual sections of the study. Furthermore, the study protocol, each step of the data-recording procedure and the handling of the data as well as the study report may be subject to independent review by a Quality Assurance representative. Clinical site and study audits will be conducted as necessary to assure the validity of the study data.

## 13. STUDY ADMINISTRATION

### 13.1 Study Administrative Structure

The study administration structure is provided in [Table 9](#).

### 13.2 Ethical Conduct of the Study

The study must fully adhere to the principles outlined in “Guideline for Good Clinical Practice” ICH E6 Tripartite Guideline (January 1997), and in general, be conducted in a manner consistent with the principles described in the Declaration of Helsinki. The Investigator will ensure that the conduct of the study complies with the basic principles of GCP as outlined in the current version of 21 CFR, subpart D, Part 312, “Responsibilities of Sponsors and Investigators”, Part 50, “Protection of Human Subjects”, and Part 56, “Institutional Review Boards”.

### 13.3 Informed Consent (ICF)

A properly executed, written informed consent document, in compliance with 21 CFR, Part 50 and the ICH guidelines, will be obtained from each subject before the subject is entered into the study and before any study screening procedure is performed that involves risk. Attention will be directed to the basic elements required for incorporation into the informed consent under US Federal Regulations for Protection of Human Subjects (21 CFR 50.25[a]) and (21 CFR 50.25[b]), as necessary.

Sample ICFs will be supplied to each site. The Sponsor or its designee must review any proposed deviations from the sample ICF. The final IRB -approved document must be provided to the Sponsor for regulatory purposes.

It is the responsibility of the Investigator, or a person designated by the Investigator, to obtain written informed consent from each subject (or the subject's legally authorized representative) participating in this study after adequate explanation of the aims, methods, anticipated benefits, and potential hazards of the study. In the case where the subject is unable to read, an impartial witness should be present during the entire informed consent discussion. After the subject has orally consented to participation in the trial, the witness' signature on the form will attest that the information in the consent form was accurately explained and understood. A copy of the ICF must be provided to the subject or to the subject's legally authorized representative. If applicable, it will be provided in a certified translation of the local language.

The eCRF for this study contains a section for documenting informed subject consent, and this must be completed appropriately. Signed ICFs must remain in each subject's study file and must be available for verification by site monitors at any time. If new safety information results in significant changes in the risk/benefit assessment, the consent form should be reviewed and updated as necessary. All subjects (including those already being treated) should be informed of the new information, should be given a copy of the revised form, and should give their consent to continue in the study.

#### **13.4 Institutional Review Board**

This study is being conducted under US IND 128152. This protocol (and any modifications) and appropriate consent procedures must be reviewed and approved by an IRB. This board must operate in accordance with the current federal or local regulations. The Investigator will send a letter or certificate of IRB approval to the Sponsor (or designee) before subject enrollment and whenever subsequent modifications to the protocol are made.

#### **13.5 Dose Escalation Committee**

The DEC will perform the 24-hour safety data review for the first subject in Cohort 1 to ensure that there are no overt safety concerns before dosing the second subject. The DEC will also review the 7-day safety data for the first 2 subjects in Cohort 1 prior to dosing the remaining subjects in the cohort.

#### **13.6 Sponsor Medical Team**

The Sponsor Medical Team will consist of at least the Medical Monitor and the Sponsor Medical Lead.

After 4 subjects in Cohort 1 reach Day 42, the Sponsor Medical team will review available safety and PD data and will decide the dosing regimen for Cohort 2. The Sponsor Medical Team will also perform the 24-hour safety data review for the first subject in Cohort 2 to ensure that there are no overt safety concerns before dosing the second subject in Cohort 2. The Sponsor Medical Team will review the 7-day safety data for the first 2 subjects in Cohort 2 prior to dosing the remaining subjects in the cohort. In addition, the Sponsor Medical Team will, on an ongoing basis, review Safety and PD data.

### **13.7 Future Use of Subject Samples**

Not all the tissue and blood components obtained during this study may be required for the tests that are part of the clinical trial. Available samples may be used for additional analyses and research. This research will help to understand disease subtypes, drug response and AE, and possibly identify new drug targets or biomarkers that predict subject response to treatment. The use of the samples for internal research will be done using the guidelines defined by the FDA guidance for In Vitro Diagnostic Device Studies Using Leftover Human Specimens that are Not Individual Identifiable (issued 25 April 2006) and the European Medicines Agency Reflection Paper on Pharmacogenetic Samples, Testing and Data Handling (Doc. Ref. EMEA/CHMP/PGxWP/201914/2006; 15 November 2007). If a subject requests destruction of their tissue and blood samples and the samples have not yet been de-identified, the Sponsor will destroy the samples as described in this FDA guidance. The Sponsor will notify the Investigator in writing that the samples have been destroyed.

## **14. CONDITIONS FOR MODIFYING THE PROTOCOL**

Protocol modifications to ongoing studies must be made only after consultation between a Sponsor representative and the Investigator. Protocol modifications will be prepared, reviewed, and approved by Sponsor representatives.

All protocol modifications must be submitted to the IRB for information and approval in accordance with local requirements, and to regulatory agencies if required. Approval must be obtained before any changes can be implemented, except for changes necessary to eliminate an immediate hazard to study subjects, or when the change involves only logistical or administrative aspects of the trial (eg, change in site monitor, change of telephone number).

## **15. CONDITIONS FOR TERMINATING THE STUDY**

The Sponsor has the right to terminate the study at any time. In terminating the study, the Sponsor and the Investigator will ensure that adequate consideration is given to the protection of the subjects' interests.

## **16. STUDY DOCUMENTATION, CRFS, AND RECORD KEEPING**

### **16.1 Investigator's Files and Retention of Documents**

The Investigator must maintain adequate and accurate records to enable the conduct of the study to be fully documented and the study data to be subsequently verified. These documents should be classified into 2 separate categories as follows: (1) Investigator's study file and (2) subject clinical source documents.

The Investigator's study file will contain the protocol and protocol amendments, eCRFs, query forms, IRB and governmental approval with correspondence, sample informed consent, drug records, staff curriculum vitae and authorization forms, and other appropriate documents and correspondence.

Subject clinical source documents (usually predefined by the project to record key efficacy and safety parameters independent of the eCRFs) may include subject hospital/clinic records, physician's and nurse's notes, appointment book, original laboratory reports, ECG, electroencephalogram, X-ray, pathology and special assessment reports, signed ICFs, consultant letters, and subject screening and enrollment logs. The Investigator must keep these 2 categories of documents on file for at least 2 years following the marketing application approval date for the study treatment and for the indication being investigated or for 2 years after the development program is discontinued and the FDA notified. After that period, the documents may be destroyed subject to local regulations with prior written permission from the Sponsor. If the Investigator wants to assign the study records to another party or move them to another location, the Sponsor must be notified in advance.

If the Investigator cannot guarantee the archiving requirement at the study site for any or all of the documents, special arrangements must be made between the Investigator and the Sponsor to store these in a sealed container outside of the study site so that they can be returned sealed to the Investigator in case of a regulatory audit. When source documents are required for the continued care of the subject, appropriate copies should be made for storing outside of the study site.

